The dermatology clinics located in: King Abdullah University Hospital (KAUH), in Princess Basma Hospital, (PBH), King Talal Hospital (KTH), Princess Haya Hospital (PHH) and Prince Rashid Hospital (PRH) and King Hussein Medical Center will be visited for patients interview and data collection. The participants' privacy will be preserved throughout the study and the participants' answers will be kept strictly confidential and never associated with any personal details. This study does not involve any human biological sample. No potential risks will be associated with the participation in the current study. No special safety consideration for isotretinoin drug Except those mentioned above since it approved from 1982. Consent will be obtained from IRB.

Data analysis

After data was collected, the data was entered into Excel worksheets. The responses were coded and entered into SPSS (version 23). Descriptive statistics of categorical and continuous variables were

calculated. For the categorical variables, the frequency and percentage were calculated, while the arithmetic mean and standard deviation were calculated for continuous variables.

The differences in participants' responses were examined using the Chi-square test (between intervention and control groups) and McNamara's test (between baseline and follow up encounters) for categorical dependent variables as appropriate. For continuous dependent variables, One Way Analysis of Variance (ANOVA) test, independent samples t-test, and Wilcoxon test were performed when applicable. Both Kolmogorov-Smirnov Z and Shapiro-Wilk tests were used to test for normality of continuous variables. The statistical significance level was considered at a p-value ≤ 0.05 .

Patients Knowledge and Awareness of Isotretinoin:

The degree of knowledge and awareness of correct practice was calculated as a total score. The patient knowledge section consisted of ten different questions/items, and each item had two answers (yes/no). Items were coded according to the answer; the correct (adequate) answer was coded as one (1), while the wrong (not adequate) answer was coded as zero (0). So, the knowledge score could take the values of 0 (no knowledge) to 10 (perfect knowledge).

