Chi square test was used to measure patients' knowledge regarding isotretinoin use at baseline between intervention and control group. It was also used to measure patients' knowledge regarding isotretinoin use at follow-up between intervention and control group. To measure if there was a significant difference in the correct patient knowledge regarding isotretinoin use, the percentage of the correct response for each question was calculated for both groups in baseline and at follow-up. McNamara's test was performed to test if there was a significant difference in knowledge before the intervention and after the intervention in the intervention group, and at if there was a significant difference in knowledge between baseline and follow-up in the control group. In addition, independent t-test was used to compare the knowledge score differences (knowledge score at follow up – knowledge score at baseline) between the intervention group and the control group. Linear regression was conducted to evaluate the effect of the educational intervention on the difference in knowledge score adjusting to variables that were unbalanced at baseline.

Patients Adherence to the Recommendations

Similarly, adherence to recommendations for appropriate uses provided by clinical pharmacists for correct practice was calculated as a total score for each participant. This section consisted of 10 items for all patients, and each item had answers (yes/no). Items were coded according to the answer; the correct (adherent) answer was coded as one (1), while the wrong (not adherent) answer was coded as

zero (0). The adherence score of patients 'compliance with the recommendations ranged between 0 (least adherent) to 10 (most adherent). Average score was evaluated across the intervention and control groups (using t test).

HADS Scale

HADS questionnaire was analyzed based on the scoring system; which consists of fourteen items; seven items each for the depression and anxiety subscale. The score for each item ranges from 0 to 3, and the HADS score ranged from 0 to 21 for depression and the same applied for anxiety.

Chi square test was used to compare HADS items at baseline between intervention and control group. Besides, it was used to compare HADS items at follow-up between intervention and control group. Independent t-test was used to compare the HADS score differences (between baseline and at follow up) between the intervention group and the control group.

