very often	3 (2.9)	1 (1)	0.163
Quite Often	26 (25.2)	15 (15)	
Occasionally	56 (54.4)	59 (59)	
not at all	18 (17.5)	25 (25)	
I get a sort of frightened feeling as if something awful is about to happen			
very definitely and quit badly	10 (9.7)	5 (5)	0.577
yes, but not too badly	30 (29.1)	27 (27)	
a little, but it does not worry me	55 (53.4)	59 (59)	

not at all	8(7.8)	9 (9)	
I feel restless as I have to be on the move:			
Very much indeed	2 (1.9)	0 (0)	0.362
Quite a lot	21 (20.4)	18 (18)	
not very much	57 (55.3)	64 (64)	
not at all	23 (22.3)	18 (18)	
Worrying thoughts go through my mind:			
A great deal of the time	9 (8.7)	4 (4)	0.432
A lot of the time	38 (36.9)	35(35)	
From time to time, but not too often	54 (52.4)	57 (57)	
not occasionally	2 (1.9)	4(4)	
I get sudden feelings of panic			
Very often indeed	2 (1.9)	0 (0)	0.493
Quite often	6(5.8)	4 (4)	
Not very often	35 (34)	34 (34)	
not at all	60(58.3)	62 (62)	
I can sit at ease and feel relaxed:			
Definitely	12 (11.7)	11 (11)	0.674
usually	47 (45.6)	54(54)	
Not Often	43 (41.7)	34 (34)	
not at all	1 (1)	1(1)	
I feel as if I am slowed down			
Nearly all the time	1 (1)	1 (1)	0.871
very often	19 (18.4)	15 (15)	
sometimes	73 (70.9)	76 (76)	
not at all	10 (9.7)	8 (8)	
I still enjoy the things I used to enjoy:			
definitely as much	17 (16.5)	12 (12)	0.33
not quite so much	43 (41.7)	54 (54)	
only a little	36 (35)	30 (30)	
hardly at all	7 (6.8)	4 (4)	
I have lost interest in my appearance			
Definitely	0 (0)	1 (1)	0.269
I do not take as much care as I should	2 (1.9)	0 (0)	
I may not take quite as much care	16 (15.5)	11 (11)	
I take just as much care as ever	85 (82.5)	88 (88)	
I can laugh and see the funny side of things:			
As much as I can always could	31 (30.1)	31 (31)	0.461
Not quite so much now	42 (40.8)	49 (49)	
Definitely not so much now	29 (28.2)	19 (19)	
not at all	1 (1)	1 (1)	
I look forward with enjoyment to things:			

As much as I ever did	36 (35)	27 (27)	0.012
Rather less than I used to	35 (34)	56 (56)	
Definitely less than I used to	31 (30.1)	16 (16)	
Hardly at all	1 (1)	1 (1)	
I feel cheerful:			
Most of the time	12 (11.7)	10 (10)	0.456
Sometimes	49 (47.6)	57 (57)	
Not often	41 (39.8)	33 (33)	
Not at all	1 (1)	0 (0)	
I can enjoy a good book or radio or TV program:			
Often	21 (20.4)	15 (15)	0.717
Sometimes	45 (43.7)	47 (47)	
Not often	25 (24.3)	28 (28)	
Very seldom	12 (11.7)	10 (10)	

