The average difference in anxiety score (difference between baseline and follow up) was not significant between intervention and control group (P-value=0.238) Similarly, the average difference in depression score was not significant between intervention and control group (P-value=0.323).

HADS score categories for both anxiety and depression subscales were not associated with the intervention control status at baseline nor at follow up. **Table 7** summarizes the results for follow-up.

Table 7: Comparison between intervention and control groups in HADS percentages at baseline and follow-up

	HADS-baseline (%)		P-value	HADS-follow up (%)		P-value
	Intervention	Control		Intervention	Control	
Anxiety score						
less than 8	45.60	55	0.283	49.50	55	0.536
8_11	24.30	24		26.20	27	
above 11	30.10	21		24.30	18	
Depression score						
less than 8	55.30	64	0.108	58.30	64	0.288
8_11	21.40	24		20.40	23	
above 11	23.30	12		21.40	13	

6. Patient Adherence

7. Pharmacological Adherence

The descriptive results of drug-taking behavior and the adherence at follow-up for all patients are presented in **Table 8**.

Table 8: Descriptive statistics of patient's answer to adherence questionnaire

	Intervention group	Control group
--	--------------------	---------------

	n (%)	n (%)
Do you forget taking your medication		
Never	42 (40.8)	31 (31)
Rarely	51 (49.5)	51 (51)
sometimes	10 (9.7)	18 (18)
Usually	0 (0)	0 (0)
Always	0 (0)	0 (0)
Do you stop your medication when you feel better		
Never	103 (100)	98 (98)
Rarely	0 (0)	2 (2)
sometimes	0 (0)	0 (0)
Usually	0 (0)	0 (0)
Always	0 (0)	0 (0)
Do you stop your medication when you feel worse		
Never	103 (100)	98 (98)
Rarely	0 (0)	2 (2)
sometimes	0 (0)	0 (0)
Usually	0 (0)	0 (0)
Always	0 (0)	0 (0)
Do you run out of your medication		
Never	67 (65)	43 (43)
Rarely	31 (30.1)	48 (48)
sometimes	5 (4.9)	9 (9)
Usually	0 (0)	0 (0)
Always	0 (0)	0 (0)
Do you adhere to lifestyle recommendations		
Never	0 (0)	1 (1)
Rarely	1 (1)	0 (0)
sometimes	2 (1.9)	1 (1)
Usually	51 (45.5)	78 (78)
Always	49 (47.6)	20 (20)

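### Fourteen unordered HADS item tests with no multiplicity rule flag two items that differ in spread, not level, and no baseline-adjusted HADS score comparison is planned

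*Combined protocol and SAP*

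**What the plan says.** The HADS Scale subsection of Data analysis describes an instrument "which consists of fourteen items; seven items each for the depression and anxiety subscale" and adds: "The score for each item ranges from 0 to 3". It sets out three layers of comparison.

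- **Items.** "Chi square test was used to compare HADS items at baseline between intervention and control group". The same test is repeated later: "Besides, it was used to compare HADS items at follow-up between intervention and control group".
- **Subscale scores.** "Independent t-test was used to compare the HADS score differences (between baseline and at follow up) between the intervention group and the control group".
- **Bands.** Each score is cut into normal, borderline and abnormal, and a chi-square test compares the arms at baseline and again at follow-up.

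The general rule is: "The statistical significance level was considered at a p-value ≤ 0.05". No ordinal test, exact test or multiplicity rule is given for the items. Regression adjustment for variables unbalanced at baseline is described for the knowledge score only.

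Table 6 prints fourteen follow-up P-values. Two are at or below 0.05: the tense item (0.006) and the item "I look forward with enjoyment to things" (0.012). For change in score the results text gives P=0.238 (anxiety) and P=0.323 (depression). On the bands it says: "HADS score categories for both anxiety and depression subscales were not associated with the intervention control status at baseline nor at follow up".

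**The concern.** An unordered chi-square asks whether two answer distributions differ in any way. For a symptom item scored 0 to 3, the useful question is whether one arm scores higher. The two can disagree, and a reader who sees 0.006 and 0.012 beside mood items will tend to take them as a difference in level. With fourteen tests at 0.05, one or two low values are also not surprising.

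The second issue is baseline. In Table 7 the intervention arm starts with more patients above 11 on both subscales. The follow-up item and band tests make no use of that. The change-score t-test does use baseline, but a change score is not the same as adjustment: when the correlation is imperfect, the arm that starts higher tends to show the larger apparent fall. Appendix 2 says isotretinoin may cause depression and that patients should be monitored for it, so HADS merits an interpretable estimate. The report gives no HADS mean by arm, no between-arm difference and no confidence interval.

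**Working it through.** **1. Reproduce Table 6.** Pearson chi-square, 2×4, 3 df, on the printed counts (intervention n=103, control n=100). All fourteen P-values reproduce to rounding.

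- Tense, most to least severe: 4/20/54/25 v 2/7/75/16. Expected counts are 3.04/13.70/65.45/20.80 v 2.96/13.30/63.55/20.20. The sum of (O−E)²/E is 12.28, P=0.0065.
- Look forward, least to most severe: 36/35/31/1 v 27/56/16/1. Chi-square 10.88, P=0.0124.

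**2. Check the scoring.** With answers scored 0 to 3, the item means sum to 7.95 v 7.21 (anxiety) and 7.17 v 6.86 (depression). Pooled over 203 patients these give 7.586 and 7.015, which match the overall follow-up means in the text.

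**3. Level and spread for the two items.**

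| Item | Mean (int. v control) | Difference (95% CI) | Mann-Whitney P | SD (int. v control) | Levene P | Score ≥2 | Score 0 |
|---|---|---|---|---|---|---|---|
| Tense | 106/103=1.03 v 95/100=0.95 | 0.08 (−0.11 to 0.26) | 0.53 | 0.77 v 0.56 | 0.001 | 24 v 9 | 25 v 16 |
| Look forward | 100/103=0.97 v 91/100=0.91 | 0.06 (−0.15 to 0.27) | 0.64 | 0.83 v 0.68 | 0.002 | 32 v 17 | 36 v 27 |

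The intervention arm has more high scores and also more zeros, so the means barely move.

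**4. Multiplicity.** If the fourteen tests were independent, P(at least one false positive) = 1 − 0.95¹⁴ = 0.51. Correlated items, which are likely within a subscale, would lower this. Holm on the rebuilt values: 14 × 0.00649 = 0.091 and 13 × 0.01241 = 0.161. On the rank test the smallest P is 0.032, for the butterflies item (mean 1.14 v 0.92; chi-square P=0.163), and 14 × 0.0316 = 0.44. No item survives on either test.

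**5. Sparse cells.** Eleven of the fourteen items have at least two of eight expected counts below 5; the smallest is 0.49. Monte Carlo exact P-values (20,000 tables) for the two flagged items are 0.005 and 0.008, slightly below the printed ones.

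**6. Baseline in Table 7.** Depression above 11: 23.3% v 12% (24/103 v 12/100), three-band P=0.108. Anxiety above 11: 30.1% v 21% (31/103 v 21/100), three-band P=0.283. Baseline means by arm are not given.

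**7. Change score against baseline adjustment.** Let B and F be the baseline and follow-up SDs and r their correlation.

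- Change-score variance: B² + F² − 2rBF.
- Baseline-adjusted variance: F²(1 − r²).

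The pooled SDs in the text are 4.159 and 3.28 (anxiety) and 3.709 and 3.1029 (depression). The documents do not give r; 0.3 to 0.7 is assumed.

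- Anxiety, r=0.3: 10.76 × 0.91 / (17.30 + 10.76 − 8.19) = 9.79/19.87 = 0.49.
- Anxiety, r=0.7: 10.76 × 0.51 / (28.06 − 19.10) = 5.49/8.96 = 0.61.
- Depression, r=0.3: 9.63 × 0.91 / (13.76 + 9.63 − 6.91) = 8.76/16.48 = 0.53.
- Depression, r=0.7: 9.63 × 0.51 / (23.38 − 16.11) = 4.91/7.27 = 0.68.

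**8. Follow-up scores without adjustment.** Using the pooled follow-up SD, the standard error is SD × √(1/103 + 1/100) = SD × 0.140.

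- Anxiety: difference 0.74, SE 0.46, P about 0.11.
- Depression: difference 0.31, SE 0.44, P about 0.48.

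**The case against.** The best defence is that nothing false is claimed. The text names neither item, reports the change-score and band comparisons as not significant, and treats HADS as null. The unadjusted follow-up differences in step 8 are also null, and nothing shows that a better model would overturn that. All of this stands, and it limits the point to how Table 6 is read and how well HADS is estimated.

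Several stronger readings are tempting and are not supported.

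- **Baseline HADS is ignored.** It is not: the plan compares change from baseline and compares bands at baseline. Only the follow-up item and band tests leave baseline out.
- **The arms were clearly unbalanced.** The doubling above 11 on depression is one band of one subscale, picked after seeing the data. Its 2×2 P is 0.035, but the planned three-band test gives 0.108.
- **Sparse cells produced the two low P-values.** The exact values are slightly smaller, so they did not.
- **The two results are pure artefact.** The distributions do differ in spread. The valid objections are that spread is not level, and that neither result survives correction.
- **The butterflies item is a missed signal.** Its 0.032 becomes 0.44 under the same standard that removes the other two.

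**Conclusion.** The point holds as a matter of method and presentation. Fourteen unordered tests with no multiplicity rule yield two nominal results that show no shift in mean level and do not survive Holm (0.09 and 0.16). A reader might infer from Table 6 that the intervention arm had worse mood on those items; the counts do not support that.

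For the subscale scores, a t-test on change is a weaker choice than baseline adjustment. Its variance is larger, and it does not remove whatever imbalance existed at baseline. The ratios of 0.49 to 0.61 and 0.53 to 0.68 rest on the assumed correlation and on using SDs pooled over both arms as within-arm SDs. The adjusted result cannot be computed from the documents, because baseline means by arm and the correlation are missing. The HADS conclusion may well stay null; the gain would be a more precise estimate with an interval.

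**What to change.** Keep Table 6 as counts and percentages and remove its P-values; drop the matching item tests at baseline. Replace the change-score t-test with one linear regression per subscale: follow-up score on arm plus baseline score of the same subscale. Report the adjusted mean difference with its 95% CI, together with baseline and follow-up means and SDs by arm. The three-band table can stay as description.

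The cost is a re-analysis of data already collected. What is lost is the item-level P-values, including the evidence of wider spread on two items, which the counts still show.

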After the informed consent (see appendix 1) is taken from each patient who agreed to participate in the study, the participants will be randomly assigned to either an intervention group or a control group. Intervention group will consist of the patients who will receive the educational process (recommendations) about isotretinoin by clinical pharmacists additionally to the usual routine care (education about isotretinoin provided by the physician). Control group will consist of the patients who will receive the usual routine care. Both patients and physicians are unaware of patients' assignment in both groups.

The main task of the clinical pharmacist is to educate patients in intervention group by providing them all information about isotretinoin that can serve the patient during the treatment period, which includes: the degree of the importance of adherence to the drug and the recommendations, the correct method of taking it, the importance, and when, of doing periodic laboratory tests (lipid profile, liver enzyme test, and pregnancy test), and explanation of common side effects, how to avoid and deal with them, and what are the cases in which the drug should be stopped. The detailed information on the recommendation for managing side effects that will be used to educate the patients are provided in Appendix 2.

Patient's adherence to the recommendations, awareness and side effects managements for both groups will be measured through a set of questions adapted from a validated questionnaire after one month and three months of isotretinoin initiation (Appendix 3). The validated questionnaire was adopted from a previous study on patients' knowledge about isotretinoin therapy use in Jordan. The permission to use the questionnaire was obtained from the researcher.

The questionnaire is composed of 41 questions related to: demographics, side effects, physician and clinical pharmacist practice, recommendations and contraindications according to current guidelines, and patients' commitment. In addition, the Hospital Anxiety and Depression Scale (HADS) [22], will be used to evaluate depressive and anxiety symptoms at baseline and during the follow up period in each group. Finally, clinical improvement in acne will be evaluated three months after initiating the treatment from the view of physicians as well as the patients themselves.

Location and safety considerations

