I adhere to make lipid profile test during isotretinoin use			
yes	102 (99)	98 (98)	0.618
no	1 (1)	2 (2)	
I adhere to use sunblock when going out during isotretinoin use			
yes	98 (95.1)	91 (91)	0.244
no	5 (4.9)	9 (9)	
I adhere to take isotretinoin with fatty foods			
yes	88 (85.4)	62 (62)	< 0.001
no	15 (14.6)	38 (38)	
I adhere not to donate blood during isotretinoin use			
yes	103 (100)	43 (43)	< 0.001
no	0 (0)	57 (57)	
I adhere not to make laser or wax during isotretinoin use			

yes	87 (84.3)	51 (51)	< 0.001
no	16 (15.7)	49 (49)	

Results showed that 86.4% of the intervention group compared to 69% of control group were adherent to the use of eye drop, and the difference was statistically significant (P-value=0.003). The adherence to using body lotion was higher in the intervention group (46.6%) compared to the control group (28%) with a P-value=0.006. On the other hands, there were no significant differences between both groups regarding the use of lip balm and sunblock.

For the two questions about adherence to laboratory monitoring (i.e., the liver function test or the lipid profile test), the rate of adherence was high in both group (99% for the intervention group and 98% for the control group) with no significant statistical difference.

The results of responses to the last three questions about adherence (taking the medication with or after fatty meals, adherence to not donate blood, and not to make laser or wax during treatment) were significantly different between the control and intervention group with P-value <0.001.

5. HADS Scale

HADS-Anxiety score and HADS-Depression score were tested at baseline and at follow-up after three months. At baseline, the mean HADS-Anxiety score for both groups was 7.8079 ± 4.159 , which slightly improved to 7.5862 ± 3.28 at follow-up, which was statistically not significant. Likewise, the mean HADS-Depression score was 6.773 ± 3.709 , while at follow-up it became 7.0148 ± 3.1029 and it was statistically not significant. The responses for intervention and control group at follow-up (intervention vs. control group) are indicated in **Table 6**.

Table 6: HADS anxiety and depression score at follow-up

	Intervention group n (%)	Control group n (%)	P-value
I feel tense or 'wound up.'			
most of the time	4 (3.9)	2 (2)	0.006
a lot of the time	20 (19.4)	7 (7)	
from time to time	54 (52.4)	75 (75)	
not all time	25 (24.4)	16 (16)	
I get a sort of frightened feeling like 'butterflies' in the stomach:			

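### HADS change is compared by an unadjusted t-test: valid, but its variance is at least about 1.6 (anxiety) and 1.4 (depression) times that of a baseline-adjusted analysis

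*Combined protocol and SAP*

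**What the plan says.** The study is randomised: "the participants will be randomly assigned to either an intervention group or a control group". Under Data analysis, HADS Scale, item responses and score categories are compared by chi-square test. For the scores themselves, "Independent t-test was used to compare the HADS score differences (between baseline and at follow up" between the arms. No HADS model contains the baseline score. The only regression in the plan is for the knowledge-score change, adjusted for variables unbalanced at baseline.

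Results section 5 gives means and SDs over both arms combined. For anxiety, "the mean HADS-Anxiety score for both groups was 7.8079 ± 4.159" at baseline, "which slightly improved to 7.5862 ± 3.28 at follow-up, which was statistically not significant". For depression, "the mean HADS-Depression score was 6.773 ± 3.709" at baseline, "while at follow-up it became 7.0148 ± 3.1029 and it was statistically not significant".

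The between-arm comparison of anxiety change "was not significant between intervention and control group (P-value=0.238"; the depression counterpart has P = 0.323. Neither comes with an estimate, a direction or an interval. Table 6 ("HADS anxiety and depression score at follow-up") gives item counts by arm at follow-up only. Table 7 gives category percentages by arm at both times. Arm-level baseline means are not printed.

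**The concern.** A change score subtracts the whole baseline value, which fixes the slope of follow-up on baseline at 1. The least-squares slope is r × (follow-up SD / baseline SD), where r is the correlation between the two scores. Because both SDs fall, that slope must be below 1: at most 0.79 for anxiety and 0.84 for depression, and about 0.4 for either at an assumed r of 0.5.

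Two things follow. The comparison is noisier than it need be, although the baseline score is already collected. And if the arms differed by chance at baseline, raw change removes more of that gap than baseline predicts at follow-up, so the arm that started worse tends to look as if it improved more.

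For a null result the interval is what tells the reader which differences are excluded. Here no interval is given, and the method would make it wider than necessary.

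**Working it through.** **1. Reproduce the printed means.** Score the Table 6 items 0–3, reversing the positively worded ones, and add, in table order:

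- Anxiety, intervention: 106+117+145+105+157+53+136 = 819; 819/103 = 7.95.
- Anxiety, control: 95+92+128+100+139+42+125 = 721; 721/100 = 7.21.
- Depression, intervention: 114+136+20+103+100+134+131 = 738; 738/103 = 7.17.
- Depression, control: 109+126+14+90+91+123+133 = 686; 686/100 = 6.86.

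Pooled: (819+721)/203 = 7.5862 and (738+686)/203 = 7.0148, exactly as printed. The follow-up gaps (intervention minus control; higher is worse) are g2 = +0.74 for anxiety and +0.31 for depression.

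**2. Variance floor, needing no correlation.** With baseline SD s1, follow-up SD s2 and k = s1/s2:

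- Var(change) ∝ s1² + s2² − 2·r·s1·s2
- Var(ANCOVA) ∝ s2²·(1 − r²)
- Ratio = 1 + (k − r)²/(1 − r²)

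For k > 1 the ratio is smallest at r = 1/k, where it equals k².

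- Anxiety: (4.159/3.28)² = 1.61, at r = 0.79.
- Depression: (3.709/3.1029)² = 1.43, at r = 0.84.

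These use pooled SDs. Within-arm SDs consistent with the follow-up gaps and printed P-values give floors of 1.57–1.63 and 1.41–1.43. Charging ANCOVA for baseline imbalance as well, the lowest values found are 1.56 and 1.41.

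**3. Interval width at an assumed r = 0.5.**

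- Anxiety: Var(change) = 17.30 + 10.76 − 13.64 = 14.41; Var(ANCOVA) = 10.76 × 0.75 = 8.07; ratio 1.79. Half-width 1.97 × √(14.41 × (1/103 + 1/100)) = 1.05, against 0.79 for ANCOVA (0.79–0.80 with within-arm SDs and the imbalance allowance).
- Depression: 11.88 against 7.22; ratio 1.64. Half-width 0.95 against 0.74 (0.75 with the allowance).

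**4. What could happen to the anxiety estimate.** From P = 0.238 (t = 1.18, 201 df) the change difference is d = ±1.18 × √(Var(change) × (1/103 + 1/100)), and the implied baseline gap is g1 = g2 − d. The ANCOVA estimate is g2 − b·g1, with b = r·w2/w1 and w1, w2 the within-arm SDs. Its squared SE is w2²(1 − r²)(201/200)(1/103 + 1/100 + g1²/(201·w1²)). The sign of d is not printed, so both are shown.

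| r | d < 0 (favours intervention): d; g1; ANCOVA; P | d > 0 (favours control): d; g1; ANCOVA; P |
|---|---|---|
| 0.5 | −0.63; 1.37; +0.20; 0.62 | +0.63; 0.11; +0.70; 0.08 |
| 0.75 | −0.45; 1.20; +0.03; 0.92 | +0.46; 0.28; +0.58; 0.06 |
| 0.8 | −0.41; 1.15; +0.01; 0.97 | +0.42; 0.33; +0.54; 0.053 |
| 0.85 | −0.36; 1.11; 0.00; 0.99 | +0.37; 0.37; +0.49; 0.044 |
| 0.9 | −0.31; 1.05; −0.01; 0.98 | +0.31; 0.43; +0.44; 0.030 |

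How high r can be: the pooled anxiety change of −0.22 is printed as not significant, which by a paired t-test at 0.05 needs r below about 0.93. The right-hand column therefore cannot be cut off at 0.8.

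**5. What Table 7 adds.** At baseline, anxiety above 11 was 30.1% v 21% and below 8 was 45.6% v 55% (intervention v control). At follow-up the figures were 24.3% v 18% and 49.5% v 55%. The intervention arm looks worse at both times, by less at follow-up. A normal approximation with cuts at 7.5 and 11.5 puts the baseline gap at 1.0–1.2. In the left-hand column that fits only r of about 0.75 or more, where the ANCOVA estimate is +0.03 to −0.005, that is, zero.

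**6. Depression.** For r from 0 to 0.8, ANCOVA P is 0.24–0.95 over both signs of d. The same paired-test argument caps r at about 0.88, where the smallest P is about 0.21.

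**The case against.** The strongest reply is that this is an efficiency preference on an outcome the study was not sized for. The sample size rests on adherence, HADS is an additional measure, the t-test is unbiased under randomisation, and no HADS benefit or harm is claimed. All of that stands, and it limits the weight of the point. It does not remove it: the gain costs no data and the floor needs no assumed correlation.

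A second reply is that much of the difficulty is missing estimates and intervals, which a CI on the existing change score would supply. That is also fair, but such an interval would still be the wider one.

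Three stronger readings are tempting, and the documents do not support them.

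- A reader might infer that ANCOVA would reverse the anxiety result from favouring intervention to favouring control. The sign of the raw difference is not printed. The Table 7 approximation is rough: with the printed follow-up mean and SD it predicts 11.6% above 11, while Table 7 pools to 21.2%. At the correlations that fit its baseline gap, the adjusted estimate is about zero. The +0.20 at r = 0.5 has an SE of 0.40.
- A reader might infer that significance cannot change under any correlation. That fails for anxiety in the right-hand column of the table once r passes about 0.8.
- A reader might take the point to concern isotretinoin and mood. Both arms take the drug; the contrast is pharmacist education.

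**Conclusion.** The point holds as a matter of efficiency and estimation, not validity. The change-score t-test has at least about 1.6 times (anxiety) and 1.4 times (depression) the variance of ANCOVA. For anxiety, 203 patients analysed this way carry the information of at most about 126 under ANCOVA (203/1.61).

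If the raw anxiety change favours intervention, adjustment would pull the estimate towards zero. Neither the sign nor the size can be settled without arm-level baseline means. The non-significant conclusion probably stands for both subscales. The exception is anxiety with r above about 0.8 and a raw change favouring control, where ANCOVA P would be about 0.02–0.04; Table 7 makes that sign less likely but does not exclude it.

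The figures assume equal SDs in the two arms, a common slope and two-sided testing. The correlation is not given, so every figure other than the floors depends on the r shown with it.

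**What to change.** For each HADS subscale, fit follow-up score on arm plus that subscale's own baseline score. Report the adjusted difference with its direction and 95% CI. Print the baseline and follow-up mean and SD by arm, so that the sign and size of any baseline gap can be seen. Because results are already reported, label the analysis post hoc and keep the change-score t-test as a sensitivity analysis, with its own estimate and interval.

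The cost is one regression per subscale on data in hand and a few lines in the HADS analysis and results text. No new data are needed.
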